### **2.4.2 Known Potential Benefits**

Narrowing surgical resection in cases that do well on neoadjuvant or induced chemoimmunotherapy preserves lung function, potentially reducing the risk of perioperative complications, and death. It protects the patient's general state of health, reduces the incidence of long-term non-tumor deaths, maintains a high physical strength score, facilitates adjuvant therapy follow-up, and may result in a long-term survival benefit for the patient.

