### **2.4.2 Assessment of potential risks/benefits**

It has been shown in retrospective studies that total pneumonectomy is only performed when lobectomy is difficult to achieve R0 resection and is associated with higher perioperative complications and mortality than lobectomy, with a significant impact on the patient's general state of health and strength scores, which may contribute to impaired long-term survival. In patients who do well on neoadjuvant or induction therapy, conversion to lobectomy can potentially reduce the incidence of perioperative adverse events, reduce the risk of immediate and long-term non-tumor death, protect the patient's general health and strength scores, and increase the patient's chances of receiving postoperative adjuvant therapy, thereby reducing the risk of tumor-related death.

Risk-minimizing measures: Select patients with good results of neoadjuvant or induction therapy according to strict admission criteria, review the tracheoscopic biopsy before surgery to clarify the status of the bronchus to be preserved, take frozen pathology to clarify the status of the nearest incision margins during the surgery to decide the actual surgical method, and maintain adjuvant therapy after the surgery to minimize the possibility of increasing the risk of local recurrence. Postoperatively, the patient's vital signs, drainage, and air leakage were closely observed to ensure perioperative safety.

Preoperative and intraoperative reassessment

1 Bronchoscopic biopsy of bronchial mucosa to be preserved/EBUS to assess the condition of the outer wall of the preserved bronchus.

2 In cases of main pulmonary artery invasion prior to neoadjuvant therapy, intraoperative

freezing is performed to assess the status of the arterial wall at the site of original invasion.

3 For cases with transverse fissure invasion, pulmonary fissure margins were frozen for pathologic evaluation.

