### **5.3 Determination of sample size**

This study is a prospective observational clinical study, and the purpose of the study is to evaluate the feasibility and long-term outcome of pneumonectomy to lobectomy after neoadjuvant or induction chemoimmunotherapy for locally progressive non-small cell lung cancer. Due to the lack of previous reference data, the sample size was not calculated based on hypothesis testing, and 50 patients were enrolled.

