### **6.4 Methods of Study Subject Allocation**

This study is a single-arm clinical trial and does not involve the allocation of study subjects to the enrollment group.

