## 10. Statistical analysis

### 10.1 General methodology

All statistical analyses were performed using R software, and hypothesis tests were standardized using two-sided tests, giving the test statistic and its corresponding p-value.  $p<0.05$  was considered statistically significant, and 95% confidence intervals were set as required.

Statistical description: All indicators are described according to their nature. Qualitative indicators are expressed as frequencies and percentages of categories; metrics provide the number of cases, mean, standard deviation, median, minimum and maximum values.

Statistical inference: For overall survival time and disease-free survival time, overall survival curves and disease-free survival curves were plotted using the Kaplan-Meier method; risk differences between survival and disease-free survival were assessed using the Log-Rank test; multivariate analyses were performed using the Cox proportional risk model to assess the effect of subgrouping (surgical modality) and other prognostic factors on survival and disease-free survival. survival and disease-free survival. The t-test was used for measures that were normally distributed, and the rank-sum test was used for measures that were not normally distributed; the chi-square test was used for between-group comparisons of count data, and the Fisher exact probability method was used when necessary.

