### 10.2 Analysis of Primary and Secondary Study Endpoints

#### Primary Endpoints

Overall survival time (in months): Overall survival curves were plotted using the Kaplan-Meier method; the difference in survival risk between the two groups was assessed using the Log-Rank test with 95% confidence intervals; multivariate analyses were performed using the Cox proportional risk model to assess the effect of subgrouping (surgical procedure) and other prognostic factors on the survival risk, and 95% confidence intervals were given for each factor. A multivariate analysis using the Cox proportional risk model was performed to assess the effect of grouping factors (surgical modality) and other prognostic factors on survival risk with 95% confidence intervals for each factor.

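### Survival is compared by type of operation with an unadjusted log-rank test and a Cox 'effect', although good response steers patients to the smaller operation and no response variable is defined

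*Protocol*

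**What the plan says.** **Who gets which operation.** Protocol section 6.4 states: "This study is a single-arm clinical trial and does not involve the allocation of study subjects to the enrollment group". Section 7.1.1 has every patient reassessed after chemoimmunotherapy and then allows pneumonectomy, lobectomy, combined lobectomy or sleeve lobectomy. The two sections numbered 2.4.2 tie the smaller operation to good response: "Narrowing surgical resection in cases that do well on neoadjuvant or induced chemoimmunotherapy preserves lung function", and "In patients who do well on neoadjuvant or induction therapy, conversion to lobectomy can potentially reduce the incidence of perioperative adverse events". The risk-minimising measures in the second of these repeat the selection on good treatment results and add that frozen margins settle the final procedure.

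**What is analysed.** Section 10.1 says that "hypothesis tests were standardized using two-sided tests" and that p<0.05 "was considered statistically significant, and 95% confidence intervals were set as required". For survival it plans Kaplan-Meier curves and a log-rank test, and then "multivariate analyses were performed using the Cox proportional risk model to assess the effect of subgrouping (surgical modality) and other prognostic factors". Section 10.2 repeats this for overall survival under its heading for primary endpoints ("the difference in survival risk between the two groups was assessed using the Log-Rank test with 95% confidence intervals") and again for disease-free survival. Neither section defines the two groups.

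**What is collected.** The items and endpoints listed in sections 1.1, 5.1, 5.2 and 9.1 contain no radiological response, downstaging or pathological response. The visit table in section 7.5 goes from screening straight to the peri-operative period.

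**The concern.** Response to induction plausibly affects two things at once: which operation the patient receives and how long the patient lives. A comparison of survival by operation that ignores response gives part of the responders' better outlook to the operation. The error has a known direction, towards lobectomy.

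The rationale of the study is that a smaller resection may improve survival through fewer complications and better access to adjuvant therapy, and section 2.2 says that the work should lay the foundation for clinical application. A survival difference produced by selection would be easily read as support for that rationale. The word 'effect' in the analysis text invites this reading, and nothing in the protocol warns against it or limits the comparison to description.

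**Working it through.** **No planned figure to reproduce.** Section 5.3 states that "the sample size was not calculated based on hypothesis testing, and 50 patients were enrolled". The protocol gives no response rate, conversion rate, event count or effect size, so the size of the bias can only be shown over a range of assumptions.

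**Inputs from the protocol:** 50 patients, follow-up of 3 years (section 8.3), two-sided 0.05.

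**Assumed inputs:**
- The operation has no effect (true hazard ratio 1.00).
- 60% of patients are responders.
- 3-year survival of non-responders is 50%, with exponential times and all patients followed for 36 months.
- The hazard ratio for death, responder against non-responder, is 0.7, 0.5 or 0.3.
- The probability of lobectomy in responders against non-responders is 0.7 v 0.5 (weak selection), 0.8 v 0.3 (moderate) or 0.9 v 0.1 (strong).

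**Step 1: one case by hand.** With a response hazard ratio of 0.5, 3-year survival of responders is 0.5^0.5 = 0.707. Of 50 patients, 30 respond and 20 do not. Under strong selection:
- Lobectomy: 27 responders and 2 non-responders. Survival = (27 × 0.707 + 2 × 0.5)/29 = 0.69.
- Pneumonectomy: 3 responders and 18 non-responders. Survival = (3 × 0.707 + 18 × 0.5)/21 = 0.53.

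A gap of 16 percentage points appears although the operation does nothing. Under weak selection (21 + 10 against 9 + 10 patients) the same sums give 0.64 against 0.60.

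**Step 2: simulation over the range.** The apparent hazard ratio for lobectomy comes from an unadjusted Cox fit to 60,000 simulated patients. The rejection rate of the log-rank test comes from 3,000 trials of 50 patients.

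| Response HR | Selection | Apparent HR | Log-rank rejects | Mean deaths |
|---|---|---|---|---|
| 0.7 | weak | 0.93 | 5.4% | 21.6 |
| 0.7 | moderate | 0.84 | 8.4% | 21.4 |
| 0.7 | strong | 0.75 | 10.8% | 21.5 |
| 0.5 | weak | 0.86 | 6.4% | 18.8 |
| 0.5 | moderate | 0.69 | 12.8% | 18.9 |
| 0.5 | strong | 0.58 | 24.1% | 18.7 |
| 0.3 | weak | 0.77 | 8.1% | 15.6 |
| 0.3 | moderate | 0.57 | 21.8% | 15.6 |
| 0.3 | strong | 0.39 | 48.7% | 15.7 |

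The apparent hazard ratio is below 1 in every row.

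**Step 3: is response the source?** With response added to the Cox model, the hazard ratio for the operation returns to 0.97 to 1.04, and its rejection rate is 4% to 8%. In a second set-up (35 lobectomies with 90% responders, 15 pneumonectomies with 20%), giving response no prognostic value brings rejections in favour of lobectomy down to about 3%, close to the 2.5% expected in one direction.

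**Step 4: how much can adjustment deliver?** Expected deaths are few. The second set-up has 31.5 + 3 = 34.5 responders and 15.5 non-responders. With a response hazard ratio of 0.3, deaths = 15.5 × 0.5 + 34.5 × (1 − 0.5^0.3) = 7.75 + 6.48, about 14. The table gives up to about 22.

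Events needed for 80% power at a hazard ratio of 0.5 are (1.96 + 0.84)² / [p(1 − p)(ln 0.5)²], where p is the share with one operation: 66 for a 50:50 split and 78 for 70:30. With 20 deaths the power is 34% or 30%.

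In the second set-up only about 3 pneumonectomy patients respond (15 × 0.2) and 3 to 4 lobectomy patients do not (35 × 0.1). The median adjusted 95% interval around a true hazard ratio of 1 is then about 0.23 to 4.4 (response hazard ratio 0.3) or 0.26 to 3.9 (0.5).

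**The case against.** **The covariates may be settled elsewhere.** The Cox model adjusts for other prognostic factors without naming any, and such a list is commonly left to a statistical analysis plan, which is not at hand. Response is not excluded. This stands: the unnamed covariates alone are no finding, and the Cox estimate is biased only if response is left out. It does not rescue the log-rank test, which is unadjusted as written, or the 'effect' wording.

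**Response may well be recorded.** Patients are reassessed after treatment (7.1.1), the preserved bronchus is biopsied or examined by EBUS (2.4.2), the specimen goes to pathology (9.1), and section 11.5.1 requires all relevant case information on the case report form, which is not shown. A reader might infer that response will not be available at all; the protocol does not support that. What it lacks is a defined response variable or criterion.

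**The groups are an inference.** Section 7.1.1 lists several resections and also open against minimally invasive access. Lobectomy against pneumonectomy is the most plausible meaning of the two groups, but the text does not fix it. This stands, and it is a reason to define them.

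**Other things decide the operation.** Anatomy and frozen margins matter as well. That is true, so response is the main stated criterion and not the only one. Weak selection would leave little bias, as the table shows.

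**Conclusion.** The point holds in a limited form. Followed as written, the log-rank comparison of overall and disease-free survival by surgical modality is biased towards lobectomy. The Cox estimate shares the bias unless response is added. For overall survival the false-positive rate of a nominal 5% test lies anywhere from about 5% to 49% under the assumed inputs. It is near nominal if response barely affects the choice of operation or barely predicts survival, and high only if both links are strong. The protocol gives no figures that would place the trial within that range.

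A reader might infer that the plan would go on to declare that lobectomy significantly improves survival. The numbers do not support this: even in the most extreme setting of the table, about half of the trials give no significant result, and in most settings the large majority do not.

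The R0 resection rate, which sections 5.2 and 9.1 name as primary, is not touched by this point. What is at risk is the survival conclusion, which section 10.2 lists as primary. The change should be made before analysis, but it does not undermine the trial as a single-arm feasibility study.

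**What to change.** 1. In sections 10.1 and 10.2, define the two groups.
2. In section 7.1.1, define response and record it at the existing post-treatment reassessment, before the operation is chosen. Add that time point to the visit table in section 7.5. Record pathological response from the existing specimen as descriptive data only: it is known only after resection and cannot have guided the pre-operative plan.
3. Replace the effect of surgical modality with its association with survival.
4. Present overall and disease-free survival by modality descriptively, as Kaplan-Meier estimates with confidence intervals, and also by pre-operative response. Do not use a log-rank p-value as evidence of a modality effect.
5. Label any Cox model exploratory and include pre-operative response and pre-treatment stage.

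The cost is one or two case report form items, drawn from assessments that are already done, and some analysis wording. The survival comparison by modality no longer supports a significance claim. Adjusted intervals will be very wide with roughly 14 to 22 deaths under the assumed inputs, and if response and operation overlap almost completely, adjustment cannot separate them. That is why description comes first and the model second.

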### 10.2 Analysis of Primary and Secondary Study Endpoints

#### Primary Endpoints

Overall survival time (in months): Overall survival curves were plotted using the Kaplan-Meier method; the difference in survival risk between the two groups was assessed using the Log-Rank test with 95% confidence intervals; multivariate analyses were performed using the Cox proportional risk model to assess the effect of subgrouping (surgical procedure) and other prognostic factors on the survival risk, and 95% confidence intervals were given for each factor. A multivariate analysis using the Cox proportional risk model was performed to assess the effect of grouping factors (surgical modality) and other prognostic factors on survival risk with 95% confidence intervals for each factor.

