**Study Objective :**

Primary objective: to investigate the feasibility of switching to lobectomy after neoadjuvant/induced chemoimmunotherapy in patients with operable non-small cell lung cancer requiring pneumonectomy at first diagnosis (R0 resection rate of lobectomy).

Secondary objective: to investigate the perioperative and long-term outcomes of patients with operable non-small cell lung cancer who were evaluated to undergo pneumonectomy at first diagnosis and switched to neoadjuvant or induction chemoimmunotherapy and subsequent lobectomy.

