### 4. Aims of the study

Primary objective: to investigate the feasibility of conversion to lobectomy after neoadjuvant/induced chemoimmunotherapy in patients with operable non-small cell lung

cancer who are required to undergo pneumonectomy at first diagnosis (R0 resection rate).

Secondary objective: to investigate the perioperative and long-term outcomes of patients with operable non-small cell lung cancer who were evaluated to undergo pneumonectomy at first diagnosis and switched to neoadjuvant or induction chemoimmunotherapy and subsequent lobectomy.

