#### Primary study endpoints

- Tumor R0 resection rate (lobectomy)

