#### Secondary study endpoints

- Overall survival (OS, unit:month)
- Disease-free survival (DFS, unit: month)
- Surgical Evaluation Indicators.
  - Surgical time (unit: minutes), intraoperative bleeding (unit: ml), intraoperative blood transfusion (unit: ml)
  - Incidence of intraoperative accidents
  - Lymph node dissection: total number of lymph node dissection (unit: one), number of lymph node dissection stations (intrapulmonary,hilar and ipsilateral

mediastinal lymph nodes), and the number of lymph nodes cleared at each station (unit: one).

- Perioperative, 30-day, 90-day complication rates, mortality rates
- Quality of Survival and Pulmonary Function Evaluation at Admission, Discharge, 30 Days, and 90 Days
  - Quality of Life Score: Scored using the short form-36 (SF-36) and recorded on a 100-point scale.
  - Resting oxygen saturation (unit: percentage)
  - Lung function: Tidal volume, Vital capacity, Forced vital capacity, first second vital capacity.
  - Tidal volume, Vital capacity, Forced Expiratory Volume In 1s, all in ml.

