## **9. Evaluation of study outcomes**

### **9.1 Evaluation of primary and secondary outcomes**

#### Primary Study Endpoints

R0 Resection rate (lobectomy): the proportion of patients with complete tumor removal by lobectomy, as evaluated by the pathologic findings of postoperative lung cancer specimens;

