#### Secondary study endpoints

- 1) Lymph node dissection: Record the total number of lymph node dissection, the number of stations of lymph node dissection, and the number of lymph node dissection at each station during the operation, and evaluate them according to the pathologic results.
- 2) Perioperative indicators: Record the duration of surgery, intraoperative bleeding, the incidence of intraoperative accidents, evaluated by surgical records and perioperative clinical manifestations, laboratory tests, physical examination;
- 3) Postoperative short-term efficacy indicators: record the length of postoperative hospitalization (days), survival within 30 days after surgery, and evaluate through postoperative follow-up;
- 4) Perioperative complication rate: Evaluated by clinical manifestations, laboratory tests, and physical examination.
- 5) 3-year disease-free survival rate: defined as the proportion of patients without tumor recurrence or metastasis 3 years after surgery, evaluated by postoperative follow-up.
- 6) 3-year overall survival rate: defined as the proportion of patients who are still alive 3 years after surgery, and evaluated by postoperative follow-up.

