#### Secondary endpoints

Disease-free survival time (in months): Disease-free survival curves were plotted using the Kaplan-Meier method; differences in the risk of disease-free survival between the two groups were assessed using the Log-Rank test with 95% confidence intervals; multivariate analyses were performed using the Cox proportional risk model to assess the effect of subgrouping factors (surgical procedure) and other prognostic factors on the risk of disease-free survival, with 95% confidence intervals for each factor. A multivariate analysis using the Cox proportional risk model was performed to assess the effect of grouping factors (surgical modality) and other prognostic factors on the risk of disease-free survival with 95% confidence intervals for each factor.

- Surgical evaluation indicators.
- Surgical time (unit: minutes), intraoperative bleeding (unit: ml), intraoperative blood transfusion (unit: ml): all quantitative data not conforming to normal distribution, calculate the median, 25% quartile, 75% quartile, the minimum value, the maximum value, and analyze the difference between the two groups by using the rank sum test.
- Incidence of intraoperative accidents: count data, using chi-square test to analyze the difference between the two groups.
- Lymph node dissection: the total number of lymph node dissection (unit: one) and the number of lymph node dissection at each station (unit: one) were non-normally distributed measurements, and the difference between the two groups was analyzed using the rank-sum test; the number of stations of lymph node dissection (intrapulmonary, hilar, and ipsilateral mediastinal lymph nodes) was count data, and the difference between the two groups was analyzed using the chi-square test. Differences between the two groups were analyzed using the chi-square test.
- Tumor R0 resection rate: count data, using the chi-square test to analyze the difference between the two groups.
- Perioperative, 30-day, and 90-day complication rates, and mortality rates: were count data, and differences between the two groups were analyzed using the chi-square test.
- Quality of Survival and Cardiorespiratory Function Evaluation at Admission, Discharge, 30 Days, and 90 Days
- Quality of Life Score SF-36 Scale: Percentage, as a non-normally distributed measure, use rank sum test to analyze the difference between the two groups.

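### Section 10.2 makes overall survival the only primary endpoint and R0 resection secondary, reversing sections 5.2 and 9.1 and leaving the R0 (lobectomy) rate with no primary analysis

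*Protocol*

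**What the plan says.** Four places in the protocol make R0 resection the primary measure:

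- Section 1.1, Study Objective: "Primary objective: to investigate the feasibility of switching to lobectomy after neoadjuvant/induced chemoimmunotherapy", with the R0 rate of lobectomy given in brackets as the measure.
- Section 4: "Primary objective: to investigate the feasibility of conversion to lobectomy after neoadjuvant/induced chemoimmunotherapy", measured by the R0 resection rate, here without the lobectomy qualifier.
- Section 5.2, primary endpoint: "Tumor R0 resection rate (lobectomy").
- Section 9.1, primary endpoint: "R0 Resection rate (lobectomy): the proportion of patients with complete tumor removal by lobectomy", judged on postoperative pathology.

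OS is secondary in section 5.2 ("Overall survival (OS, unit:month")) and in section 9.1 ("3-year overall survival rate: defined as the proportion of patients who are still alive 3 years after surgery").

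Section 10.2 differs. Under its primary-endpoint heading there is one entry, "Overall survival time (in months): Overall survival curves were plotted using the Kaplan-Meier method", followed by a log-rank test between two groups and a Cox model with surgical procedure as the grouping factor. Under its secondary-endpoint heading it has "Tumor R0 resection rate: count data, using the chi-square test to analyze the difference between the two groups".

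Section 6.4 says the trial is single-arm with no allocation. Section 10.1 asks for frequencies and percentages for qualitative indicators, and for 95% confidence intervals where required. Section 10.5 plans subgroup analyses of the primary endpoints. Section 5.3 says the 50 patients do not come from a hypothesis-test calculation.

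**The concern.** The analysis section and the endpoint sections assign opposite ranks to the same two endpoints. A statistician who follows 10.2 will report survival by operation received as the main result of a single-arm feasibility study, and the feasibility result as a secondary between-group test. One who follows 5.2 and 9.1 finds no primary analysis for the endpoint named there. With two primary endpoints in the text, the one that answers the primary question could be chosen after the data are seen. Section 10.5 inherits the problem, because the subgroup analyses attach to whichever endpoint is taken as primary.

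**Working it through.** **1. The sections side by side**

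| Section | R0 resection | Overall survival |
|---|---|---|
| 1.1 | Primary objective (by lobectomy) | – |
| 4 | Primary objective (no qualifier) | – |
| 5.2 | Primary endpoint (by lobectomy) | Secondary, in months |
| 9.1 | Primary endpoint (by lobectomy) | Secondary, as a 3-year rate |
| 10.2 | Secondary (no qualifier), two-group chi-square | Sole primary, log-rank and Cox |

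The headings in 10.2 are intact, so the reversal is in the text itself.

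**2. Would moving the R0 line to the primary heading be enough?** No. The primary endpoint is a single-arm rate, and a between-group chi-square does not estimate it. The line also omits the lobectomy qualifier. The two groups are never defined; the only grouping factor that 10.1 and 10.2 name is the surgical procedure. If that is what is meant, and the 9.1 definition is used, pneumonectomy patients score 0% by definition and the test is empty. If the qualifier is dropped, the test compares a different endpoint.

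**3. Precision of the endpoint named in 5.2 and 9.1.** The protocol gives no expected rate, power or derived sample size, so there is no stated figure to reproduce. Inputs: n = 50 (5.3); two-sided 95% level (10.1); observed counts assumed; all 50 in the denominator assumed, because 9.1 says only that it is a proportion of patients.

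Exact (Clopper-Pearson) interval for x successes in n:

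- lower = 0.025 quantile of Beta(x, n − x + 1)
- upper = 0.975 quantile of Beta(x + 1, n − x)
- half-width = (upper − lower)/2

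| x/50 | Rate | 95% CI | Half-width (points) |
|---|---|---|---|
| 25 | 50% | 35.5 to 64.5% | 14.5 |
| 30 | 60% | 45.2 to 73.6% | 14.2 |
| 35 | 70% | 55.4 to 82.1% | 13.4 |
| 40 | 80% | 66.3 to 90.0% | 11.8 |
| 45 | 90% | 78.2 to 96.7% | 9.2 |
| 48 | 96% | 86.3 to 99.5% | 6.6 |

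**4. Effect of the denominator.** For an assumed 30 R0 lobectomies:

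- of 50 enrolled: 60.0% (45.2 to 73.6%)
- of an assumed 40 operated: 75.0% (58.8 to 87.3%)
- of an assumed 32 lobectomies: 93.8% (79.2 to 99.2%)

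**5. The primary test that 10.2 names instead.** For a log-rank test with d deaths, a share p of patients in one group and hazard ratio HR (Schoenfeld, two-sided 0.05):

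power = Φ(|ln HR| × √(d·p·(1 − p)) − 1.96)

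Deaths, shares and hazard ratios are assumptions.

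- HR 0.5, d = 25, p = 0.5: 0.693 × √6.25 − 1.96 = −0.23, power 41%.
- HR 0.5, d = 10, p = 0.8: 0.693 × √1.6 − 1.96 = −1.08, power 14%.
- HR 0.7, same two settings: 14% and 7%.

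Deaths needed for 80% power at HR 0.5 with a 1:1 split: (1.96 + 0.84)² / (0.25 × 0.693²), which rounds up to 66. That is more than the 50 patients planned.

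**The case against.** The strongest reply is that the intended primary endpoint is easy to recover. The objectives, the endpoint list and the outcome definitions all agree on R0, so 10.2 is the outlier. The mention of randomisation in section 8.2 also does not fit a single-arm trial, which suggests text carried over from a two-arm template (an inference). This shows which way to correct 10.2. It does not remove the conflict, because 10.2 is the section that governs the analysis.

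Second, R0 is not left without any analysis. Section 10.1 calls for a frequency and percentage for every qualitative indicator. That stands. What is missing is an analysis assigned to R0 by lobectomy as the primary endpoint, and a confidence interval tied to it.

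Third, the confidence-interval method and the denominator are often left to a statistical analysis plan. That is fair for the detail. But a plan cannot cure this: if it followed 10.2 it would contradict 5.2 and 9.1, and the reverse.

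Fourth, the intervals measure precision at n = 50 under assumed counts, not the effect of swapping the endpoints. This is correct. In addition, section 8.2 replaces subjects who consent but do not receive the intervention, so the number enrolled could exceed 50.

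**Conclusion.** The concern holds and must be fixed. Section 10.2 contradicts 5.2 and 9.1 on which endpoint is primary, and the only test it assigns to R0 does not estimate the endpoint defined in 9.1. This conclusion comes from the text alone and needs no assumption.

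The size of the consequence does rest on assumptions. With 50 patients in the denominator, the R0 (lobectomy) rate can be estimated to within about 9 to 15 points for rates from 90% down to 50%. The survival comparison that 10.2 puts in its place would have at most about 41% power for a hazard ratio of 0.5, over 10 to 25 deaths and a 50% to 80% share of patients in one group.

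**What to change.** In section 10.2, replace the primary-endpoint paragraph with wording such as:

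> *Primary endpoint: R0 resection rate by lobectomy, estimated as a single proportion with an exact two-sided 95% confidence interval.*

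Then:

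- State the denominator there, for example all enrolled patients with those lacking an R0 lobectomy counted as failures, and say how subjects replaced under 8.2 are counted.
- Move OS to the secondary endpoints of 10.2, and say whether survival time (5.2), the 3-year rate (9.1) or both are meant.
- Label any comparison of R0 by surgical procedure exploratory and descriptive, and define the groups.
- Point the subgroup analyses in 10.5 at the R0 (lobectomy) rate, descriptively.
- Optionally, in 5.3 keep the statement that the sample size was not derived from a hypothesis test, and add the half-width of about 9 to 15 points as precision obtained, not as the basis for 50.

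The cost is protocol wording only. No extra patients or data are needed.
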